Back pain duration	Measured in days, but categorized to an ordinal scale of 3 categories: 0-6 weeks, 6-12 weeks, >12 weeks, similar to other BACE studies (22)	Covariate in previous study (8), and found to be associated with disability in older adults (4, 6, 11, 20)
Baseline disability	Continuous. Roland-Morris disability questionnaire, 0-24 scale.	Standard covariate, given the outcome is disability. Only applicable if not using mixed models.
Pain severity last week	Continuous. Numeric rating scale 0-10.	Associated with disability in one study in older adults (4).
Expectation of recovery within the next three months	5-point ordinal Likert scale. From “I am fully recovered” to “I am worse than ever”.	Consistently associated with disability in older adults (4, 6, 11)

Statistical power consideration

The published protocol for the BACE-N study estimates that we need a total of 450 patients included in the study. Allowing a 15% dropout rate at 12 months, we will have approximately 380 participants available at 12 months.

We used the power estimation tool in Stata to determine level of statistical power. With a sample size of 450, and an estimated r^2 of 0.30 for the full model of comorbidity adjusted for covariates, we have over 90% power to detect an r^2 -change of 0.017 or higher when adding comorbidity to the model.

Handling of missing data

Missing data will be handled with multiple imputation, using 5 imputations and 10 iterations unless the missing exceeds 30% and missing at random cannot be assumed. We will use the fully conditioned specification method, and regression estimation. For variables where we are unable to use regression estimation due to computational difficulties, predictive mean matching will be used (23).

Missing values for RMDQ will be handled by replacing missing items with the mean of the answered items for the individual, if less than 30% of the items are missing.

A mixed model, which we intend to use for the primary and secondary aim, does not require variable level imputation for the outcome measure. However, missing values on item level on

the RMDQ might still be an issue. To solve this, we will replace missing items for RMDQ with the mean of the answered items for the individual, if less than 7 (30%) of the 24 items are missing.

Statistical analyses

General statistical considerations

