Analyses described in this statistical analysis plan are considered a priori analyses. Possible post-hoc exploratory analyses will be explicitly identified in the article. All analyses will be carried out by the first author using Stata version 16, under supervision from the principal investigator and the advisory statistician. The statistical tests will be 2-sided, and p-value will be reported. If the p-value is less than 0.05, the test is deemed statistically significant. 95% confidence intervals will be reported on point estimates.

Statistical analyses

Description of study flow and study sample:

The flow of participants will be reported with a flow chart. Reasons for exclusion and loss to follow-up will be provided where known. Descriptive data of the study sample will be reported using mean and standard deviation for normally distributed continuous variables, median and interquartile range for variables with skewed distribution, and with frequency and proportions for categorical variables. Normal distribution will be examined visually using histogram and QQ-plot, and statistically with the Kolmogorov-Smirnov test. Baseline characteristics will be presented in a table. See proposed tables and figures below.

Descriptive statistics will be used to present the mean and standard deviation if RMDQ is normally distributed, or median and interquartile range if RMDQ is not normally distributed, for each time point: Baseline, 3 months, 6 months, 12 months. This will also be presented graphically, similarly to van der Gaag et al (3). This graphical presentation will also be performed stratified for number of comorbidities.

A person may be a responder at one time-point and a non-responder at another. Therefore, an analysis of responders versus non-responders will be performed for each time point, using bivariate analysis for baseline characteristics (chi square test, Individual Samples T-test, or Mann Whitney U-test). Results from these analyses will be presented in text, and the table available in supplementary material.

Model choice and model building strategy:

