Model fit of GLMM will be assessed by comparing the log likelihood values and/or model fit statistics as Akaike Information Criterion (AIC) of neighboring [nested] models to determine whether the inclusion of a random slope is necessary and improves the model fit.

The results will be presented as crude and adjusted beta coefficients (B) with 95% confidence intervals (CI) as shown in table 2 and as margin plots with pairwise comparisons.

Sample size

This study contains secondary analyses embedded in the BACE-N study. The BACE-N study included a total of 452 participants which is deemed as an appropriate number of people for such a study (30). The number of subjects included for each time point (baseline, 3-, 6-, 12-, and 24 months) that answered all questions of interest in relation to the pain intensity analysis was 358, 306, 293, 281, and 248, respectively. In regard to the PASS investigation, these numbers for the same timepoints were 365, 295, 279, 272, and 230, respectively.

5. Presentation of the results

Table 1. Patient Characteristics at baseline based on classes identified by LCA (n =)

	Class 1	Class 2	Class 3	Class 4
Age (mean (SD))				
Gender (n (female))				
Education (n (%))				
Less than High School				
High School				

Higher education <4 years

Higher education > 4
years

Paid work (n (%))

Yes

No

Primary health care

practitioner (n (%))

General practitioner

Physiotherapist

Chiropractor

Pain intensity (NRS)

(mean (SD))

Symptom satisfaction

(PASS) (mean (SD))

SD – standard deviation, n – number, NRS – numeric rating scale, PASS – patient acceptable symptom state

Table 2. Estimates of fixed effects parameters from linear mixed models. Showing the association between latent classes, pain intensity (NRS) and symptom satisfaction (PASS) over 24 months.

	NRS score			PASS score		
	B	95% CI	P	B	95% CI	P
Unadjusted model						
Follow-up time points						
Baseline (ref)						
3 months						
6 months						
12 months						
24 months						
LCA class						
The Positive (ref)						
The Fearful						
The Negative						
The Hopeful						
Interaction Time x LCA						
Baseline x The Positive (ref)						
3 months x The Fearful						

3 months x The Negative

3 months x The Hopeful

6 months x The Fearful

6 months x The Negative

6 months x The Hopeful

12 months x The Fearful

12 months x The Negative

12 months x The Hopeful

24 months x The Fearful

24 months x The Negative

24 months x The Hopeful

Full model

Follow-up time points

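### The comorbidity SAP states its power for all 450 enrolled patients although it expects about 380 at 12 months; in the regression that reproduces its figure, 380 patients give about 86%, not over 90%.

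*Combined protocol and SAP*

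**What the plan says.** The place is the third SAP in the combined document (one-year course of disability and prognostic value of comorbidity, 22.03.2021), under Statistical power consideration. Its first paragraph takes the target of 450 patients from the BACE-N protocol and reduces it for loss: "Allowing a 15% dropout rate at 12 months", about 380 remain. Its second paragraph goes back to the full number: "With a sample size of 450, and an estimated r^2 of 0.30 for the full model of comorbidity adjusted for covariates", the authors report that "we have over 90% power to detect an r^2 -change of 0.017 or higher when adding comorbidity to the model". Nothing in the section says why 450 applies, or which model and time point the power refers to.

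Three other parts of the same SAP matter. General statistical considerations makes tests two-sided and sets the level: "If the p-value is less than 0.05, the test is deemed statistically significant". The modelling steps for the secondary aim fit RMDQ over time in a mixed model, with SCQ count and full SCQ score in separate models, and report the r²-change when SCQ is added. Handling of missing data says that the mixed model needs no variable-level imputation of the outcome.

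**The concern.** A section that derives an expected loss and then computes power as if nobody were lost invites the question of which number the power rests on. An r²-change calculation of this kind takes one outcome value per patient. If that value is the 12-month score, a patient without it adds nothing, and the relevant number is the one the SAP has just derived.

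At stake is how a weak or null result for comorbidity is read. The r²-change is the SAP's measure of what comorbidity adds to the covariates. A reader told that power exceeds 90% for 0.017 would treat a null finding as stronger evidence against an effect of that size than a calculation with 380 patients supports.

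**Working it through.** **Inputs from the SAP:** N = 450 for the power statement; expected N at 12 months about 380 (450 × 0.85 = 382.5, given as 380); r² of the full model 0.30; r²-change 0.017; two-sided level 0.05; one tested term per model.

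**Assumption:** the number of predictors in the power run is not stated. Total predictors from 2 to 14 were tried, and the power does not change by more than about 0.0001.

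**Formula:** partial F test for one added term.
- f² = Δr² / (1 − r² full) = 0.017 / 0.70 = 0.0243
- non-centrality λ = N × f²
- 1 numerator degree of freedom and N − p − 1 denominator degrees of freedom, where p is the number of predictors

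**Step 1, reproduce the stated figure.** At N = 450, λ = 450 × 0.0243 = 10.93 and power = 91.0%. This agrees with the SAP's statement. Reading 0.30 as the covariate-only r² (full model 0.317) gives 91.6%, which also agrees.

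**Step 2, use the SAP's own 12-month number.** At N = 380, λ = 380 × 0.0243 = 9.23 and power = 85.8%. With the covariate-only reading it is 86.6%.

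**Step 3, find where 90% is lost.** In this calculation 90% power for 0.017 needs N = 435 (425 under the covariate-only reading). A loss of 15 of 450 (3.3%) uses up the margin, against the 15% allowed.

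**Step 4, the effect detectable with 90% power.**

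| N | Δr², full-model r² 0.30 | Δr², covariate-only r² 0.30 |
|---|---|---|
| 450 | 0.0164 | 0.0160 |
| 380 | 0.0195 | 0.0190 |

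The detectable change is about 19% larger at 380 (0.0195 / 0.0164 = 1.19).

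**Step 5, does this carry over to the planned mixed model?** The SAP gives no within-patient correlation ρ, so it is assumed here over a range, as an exchangeable residual correlation. For a time-averaged SCQ effect, a patient with m scores counts as m / (1 + (m − 1)ρ) independent observations. Two cases, both with 15% loss:
- *All scores:* 380 patients with four scores and 70 with baseline only. Effective N = 380 × 4 / (1 + 3ρ) + 70.
- *Follow-up scores only:* 380 patients with three scores. Effective N = 380 × 3 / (1 + 2ρ).

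| Assumed ρ | Effective N, all scores | Power | Effective N, follow-up only | Power |
|---|---|---|---|---|
| 0.5 | 678 | 98% | 570 | 96% |
| 0.7 | 560 | 96% | 475 | 92% |
| 0.9 | 481 | 93% | 407 | 88% |

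These figures put the effective N in place of N in the formula above. They do not cover an SCQ-by-time interaction or a contrast at 12 months alone.

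**The case against.** The strongest reply is that no regression on the 12-month score alone is planned as the main analysis. RMDQ is measured at baseline, 3, 6 and 12 months, and the mixed model uses whatever scores a patient has. On that view 450 is the number entering the model and 380 only the number at its last visit. Step 5 supports this for a time-averaged effect: even with 15% lost after baseline, power is above 90% in five of the six cases.

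This part stands, and it limits the point. A reader might infer from the 86% that the planned analysis is underpowered, or that the stated power is too favourable for it. The documents do not support that. They do not rescue the stated figure either: the SAP gives no correlation, number of measurements or missing-visit pattern, and its figure is matched by a calculation with one outcome per patient. Such a calculation takes no credit for repeated measures.

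A second tempting inference comes from the latent-class SAP (21.02.2024). Its Sample size section counts patients who answered all questions of interest for the pain analysis at baseline, 3, 6, 12 and 24 months; the number "was 358, 306, 293, 281, and 248, respectively". A reader might take 281 of 452 at 12 months as the true retention and put it into the formula. But the count is already 358 of 452 at baseline, before any follow-up could be lost, so it reflects item completeness for a different analysis as well as dropout. It also postdates the comorbidity SAP, which plans multiple imputation and does not require complete answers. It is not used here.

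Finally, the effect is modest. Power at 380 stays above 80%, and the SAP will report 95% confidence intervals, from which a null result can be judged directly.

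**Conclusion.** The point holds for the calculation that reproduces the SAP's figure. There, replacing 450 by the SAP's own 380 lowers power from 91.0% to 85.8% (91.6% to 86.6% under the other reading of 0.30), so the type II error is about 14% and not below 10%. The change detectable with 90% power moves from 0.0164 to 0.0195.

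This rests on taking the power run as a one-outcome regression at 12 months, which the match at 450 makes likely but the SAP does not say. For the mixed model the power remains unstated; it could lie on either side of 90%, depending on the correlation and on whether the effect of interest is averaged over time. Severity is minor to moderate: a stated figure needs correcting, but no sample size, model or conclusion changes.

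**What to change.** Either of two changes to Statistical power consideration would settle it.

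1. Restate the figure with its model: for a single-time-point regression at 12 months with 380 patients, power is 86% for an r²-change of 0.017, or 90% for an r²-change of 0.0195. Add that this only approximates the planned mixed model, and say whether 0.30 is the r² with or without comorbidity.
2. Or calculate power for the mixed model itself, stating the assumed within-patient correlation, the 15% dropout pattern, and whether the target is a time-averaged SCQ effect or an SCQ-by-time interaction.

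The first costs two sentences and a slightly less favourable number. The second costs a short calculation or simulation and an assumption that must be stated and varied. Neither needs new data or a change of design.

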Back pain is common in all age groups (1), and one systematic review highlights that disabling back pain is more prevalent in older people than in younger people (2). The clinical course of back-related disability in older adults with back pain has not been extensively studied. Two studies suggests that improvements in disability were modest the first three months, with little to no improvements on group level after three months (3, 4). It is well documented that number of comorbidities are associated with the clinical course of back-related disability in older adults, but the prognostic value of comorbidity is still highly uncertain (5-11).

Study aim:

The primary aim of this study is to examine the clinical course of back-related disability measured at baseline, 3, 6 and 12 months after a new episode of back pain. The secondary aim is to assess the prognostic value of number and severity of comorbidity at baseline for changes in back-related disability over one year of follow-up.

Study design and method

Study design

BACE-N is based on the previously published BACE study protocol from the BACE international consortium (12). The BACE-N protocol has been published (ClinicalTrials.gov Identifier: NCT04261309).

The BACE-N study is a prospective observational cohort study with a 2-year follow-up time. This study will use data from baseline, 3, 6 and 12 months of follow-up. Design of the study was made within the framework PROGnosis RESearch Strategy (PROGRESS), which is a framework for ensuring and enhancing the quality of prognostic studies (13). The primary aim is relating overall prognosis, and the secondary aim is relating confirmatory prognostic factor research (13, 14).

Study population

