Patients aged ≥ 55 years visiting a general practitioner (GP), physiotherapist or chiropractor for a new episode of back pain are invited to participate in the study. Back pain is defined as pain located in the region from the top of the scapula to the sacrum, with or without radiating leg pain. An episode of back pain is defined as “new” if the patient has not received health care for the same back complaint during the last 6 months. The exclusion criteria were: Difficulty completing the study questionnaires due to language or cognitive difficulties, mobility impairments impeding the clinical examination (wheelchair-bound patients), had received healthcare for the same back complaint during the last 6 months (notwithstanding care initiated within the previous 4 weeks from time of baseline assessment).

Data collection

At baseline, patients receive a clinical examination and questionnaire. Patients are then given a follow-up questionnaire either through email or mail at 3-months, 6-months and 12-months follow-up.

Description of treatment received during follow-up

The study participants continue their health care in agreement with their healthcare provider regardless of inclusion in the study. This means that patients may receive education and advice, exercise therapy, massage, manipulations, mobilizations, pharmacological therapy, or additional diagnostic testing and referrals, all of which constitutes “usual” primary care (15). Treatment given is at the discretion of the healthcare provider and the patient.

Variables

Outcome measure:

Back-related disability, measured using the Norwegian, validated version of the Roland-Morris Disability Questionnaire (RMDQ) (16, 17). This is a questionnaire with 24 statements regarding abilities to perform ADL tasks, with a dichotomous yes/no answer. The answers are summed to a total score ranging from 0-24, where 0 indicates no disability and 24 indicates “maximum” disability. RMDQ has been found to measure several dimensions of back-related disability (18). We plan to use RMDQ as a continuous measure, as recommended by the PROGRESS framework (14). This will ensure easier comparability to similar studies, and easier inclusion in future meta-analyses.

RMDQ is measured at baseline, 3 months, 6 months and 12 months.

Prognostic factor measurement:

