According to the STRATOS initiative task force, a complete prespecifying of all aspects in model building is unrealistic in observational studies (24). Thus, the following will provide a framework for analysis and model building in this study, not a detailed recipe. Decisions regarding final choice of models will be made by the first author, the advisory statistician and the principal investigator.

Primary aim, clinical course of back-related disability:

Mixed models for repeated measures will be used to account for statistical dependencies. RMDQ is the dependent variable, and time and first contact health provider will be entered as fixed factors. The exact handling of time as a continuous or categorical variable depends on the distribution. Previous studies have found that the clinical course of a back episode is not linear over time (3, 25, 26). It is therefore reasonable to believe that time will have to be treated as a categorical variable, or by introducing a quadratic term, depending on its distribution. Choice of covariance matrix is dependent on data structure. Interaction between first contact health provider and time will be analysed.

Secondary aim, prognostic value of number and severity of comorbidities on the course of back-related disability:

We will fit separate models for count of comorbidity (SCQ part 1, 0-15 scale) and count and severity of comorbidity (full SCQ, 0-45). The steps are outlined below:

1. The univariate association between SCQ and RMDQ over time will be assessed with a mixed model for repeated measures. An interaction term for SCQ*time will be tested, and kept if statistically significant. We will present the crude regression estimates from this analysis.
2. A mixed model with all the covariates from Table 1 and RMDQ over time will be fitted. From this model, r^2 will be presented as a measure of prognostic value.
3. SCQ will be added to the model from step 2. The adjusted regression estimate, and the r^2 -change from step 2 to step 3 will be presented.

Previous studies have found a linear relationship between number and severity of comorbidity and disability (7, 27). Linearity between SCQ and RMDQ will be assessed with a scatter-plot. In case of non-linearity between SCQ and RMDQ comorbidity count and disability score, the following alternatives will be discussed (24, 28):

- Categorization of SCQ
- Transformation (logarithmic or cubic) of SCQ
- Fractional polynomials for SCQ
- Spline functions for SCQ

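### The disability-course SAP times follow-up from study entry for patients at different stages of an episode and tests provider-by-time without pain duration, so that contrast may be confounded

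*Combined protocol and SAP*

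**What the plan says.** All references are to the SAP dated 22.03.2021 on the one-year course of disability and the prognostic value of comorbidity, unless another is named.

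- **Aim** (Study aim): to "examine the clinical course of back-related disability measured at baseline, 3, 6 and 12 months after a new episode of back pain". Under Study design the SAP adds: "The primary aim is relating overall prognosis".
- **Entry** (Study population): an episode counts as new "if the patient has not received health care for the same back complaint during the last 6 months". This is a rule about seeking care. It sets no upper limit on how long the pain has lasted.
- **Duration** (Table 1, Covariates): "Measured in days, but categorized to an ordinal scale of 3 categories: 0-6 weeks, 6-12 weeks, >12 weeks". The rationale column says duration has been found to be associated with disability in older adults.
- **Primary model** (Primary aim, clinical course): "RMDQ is the dependent variable, and time and first contact health provider will be entered as fixed factors". The section adds: "Interaction between first contact health provider and time will be analysed". It names no covariates.
- **Secondary model** (steps 2 and 3): all Table 1 covariates enter, so duration is included there. No duration-by-time term is named.
- **Displays**: the only stratified course is by number of comorbidities. Duration is tabulated for the whole cohort and by response status, not by provider.
- **Significance** (General statistical considerations): any p-value below 0.05 is called statistically significant.

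**The concern.** Two issues follow.

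First, the wording of the aim invites the reader to take month 3 as three months after the episode began. For a patient whose pain had lasted more than 12 weeks at baseline, it is at least six months after. The average over such a cohort is legitimate, but its time origin has to be stated.

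Second, the provider-by-time interaction compares the courses of patients who chose, or were recruited through, three professions. Nothing balances these groups on how far into the episode they are. If one profession sees more recent-onset patients, and such patients change more over follow-up, the interaction can appear (or be masked) with no provider-specific difference in course. It would be tested at 0.05 in an unadjusted model, and a reader could take it as a difference between professions. As planned, the tables would not let that reader check, because neither the course by duration nor duration by provider is shown.

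**Working it through.** **1. The SAP's own figures.** It gives none for the primary model or the provider term. Its two design figures reproduce but concern study size and the secondary aim: 450 × 0.85 = 382.5, against about 380 stated; and power for an R² change of 0.017 with N = 450 and R² = 0.30 is 0.900–0.910 (0.30 as full-model R²) or 0.907–0.916 (as reduced-model R²), against over 90% stated.

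**2. Conditions for distortion.** Let c(d) be the mean 3-month RMDQ change in duration category d, the same for every provider, and let p_A(d) and p_B(d) be the duration shares for two providers. The provider-by-time contrast from the model without duration is

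Σ [p_A(d) − p_B(d)] × c(d).

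It is zero if the shares are equal or if c(d) does not vary. Both must fail for a distortion to arise.

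- *Mix differs by provider:* the documents give no data.
- *Change differs by duration:* plausible, not shown. Table 1 speaks of association with disability, not with change. The nearest support is in the external-validation SAP (28.09.2022): the Dutch model for persistent disability has a coefficient of 0.63 for duration over 3 months, alongside baseline disability. The odds ratio is exp(0.63) = 1.88. That outcome is a threshold at 6 and 12 months, not an RMDQ change.

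**3. Size under assumed values.** None of these inputs comes from the documents. Assumed 3-month changes for 0–6 / 6–12 / >12 weeks are −3 / −2.5 / −2 (mild), −4 / −2.5 / −1 (mid) and −6 / −3 / −0.5 (strong). The 0–6 and >12 week shares each differ between two providers by δ, in opposite directions, and the middle share is equal. The contrast is then δ × the gap between the outer categories (1.0, 3.0 or 5.5 points).

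Example, mid, δ = 0.20: provider A (60/20/20%) gives 0.6×(−4) + 0.2×(−2.5) + 0.2×(−1) = −3.1; provider B (40/20/40%) gives 0.4×(−4) + 0.2×(−2.5) + 0.4×(−1) = −2.5. The difference is 0.6.

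| Share difference δ | Mild | Mid | Strong |
|---|---|---|---|
| 0 | 0 | 0 | 0 |
| 10 points | 0.1 | 0.3 | 0.55 |
| 20 points | 0.2 | 0.6 | 1.1 |
| 40 points | 0.4 | 1.2 | 2.2 |

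**4. Which adjustment works.** A simulation used 40,000 patients per provider and two complete time points. It assumed baseline means of 10, 9 and 9 by duration category, and an SD of 4 both at baseline and for the added noise at 3 months. It gave these provider-by-time estimates, in RMDQ points:

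| Scenario | No duration | Duration main effect | Duration × time |
|---|---|---|---|
| Mid, 20 points | 0.59 | 0.59 | 0.01 |
| Mid, 40 points | 1.27 | 1.27 | 0.07 |
| Strong, 40 points | 2.16 | 2.16 | −0.03 |

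A main effect shifts all visits equally and cancels from the change, so it cannot help. The interaction is needed.

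**5. Parameters.** Three duration categories give 2 main-effect terms. With four visits as categories there are 3 time terms, so the interaction has 2 × 3 = 6. The total is 8; a quadratic in time would need fewer.

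**The case against.** **The primary aim is descriptive.** An overall-prognosis aim compares no exposures, so the whole-cohort course has nothing to be confounded with. Older people who consult without care in the previous six months form a coherent population, and study entry is a sensible origin for them. This stands in full. A reader might infer that the estimated course itself is biased; the documents do not support that.

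**The background evidence is not about duration.** A reader might take the Introduction's remark on modest early improvement and little afterwards as proof that patients with long-standing pain are on a plateau. It reports two studies at group level and does not break the course down by duration of pain at entry. This stands, and the remark is not relied on here.

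**Provider comparison is in neither aim, and no causal claim is made.** True, but the test is prespecified and falls under the 0.05 rule.

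**Duration is partly handled.** It enters the secondary model. The footnote to the draft results table lists duration and, with a question mark, recruiting profession together. The model text is also expressly offered as a guide that may be adapted. This permits an adjusted provider term. It does not commit to one, and it leaves the choice until the data are known.

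**Duration is one case-mix variable among several.** Age, BMI, pain severity and recovery expectation could also differ by provider. This stands, and limits what the adjusted model can claim.

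**Conclusion.** The concern holds in limited form. Time zero is study entry, the cohort spans pain of under 6 to over 12 weeks, and the provider-by-time test omits a variable that the SAP itself links to disability. The whole-cohort course is valid but should be labelled as time from study entry.

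The provider contrast may be confounded. To say that it is confounded would go further than the documents allow, because they do not show duration by provider, and a difference in RMDQ change by duration is only plausible. The distortion is zero if either condition fails. The 0.1 to 2.2 point range rests wholly on assumed changes and mixes and is not an estimate for this cohort. The change is a cheap improvement to the plan and does not repair an invalid primary result.

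**What to change.** - Keep the whole-cohort course as the primary result, and state in the aim and the results that time zero is study entry, not pain onset.
- Report the RMDQ course for each of the three Table 1 duration categories.
- Tabulate pain duration by first provider.
- Report the provider-by-time interaction as planned and again from a model that adds duration and duration × time. State that a duration main effect alone is not sufficient.
- Base any statement about different courses by provider on the adjusted model, with a caution that other case-mix differences remain.

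**Cost:** SAP wording and two extra displays. Duration is already collected and categorised. The adjusted model carries up to eight more fixed-effect parameters for a planned 450 patients, and its provider contrast will be slightly less precise.
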